The time-dependent ablation variable to be included in the analysis will be created using 3 different methods: For method 1, the ablation variable starts as 0 (no ablation) for all patients. For patients who received ablation, the ablation variable is set to 1 at the time of ablation. In method 2, the ablation variable starts as 1 for all patients who were randomized to ablation and actually received ablation. For all other patients, the ablation variable is started as 0 and set to 1 at the time of ablation if they received ablation during the trial. Method 3 has the ablation variable started as 1 for patients who were randomized to ablation. For all other patients (i.e., randomized to drug), the ablation variable is started as 0 and set to 1 at time of ablation.

Among the 3 methods described above, method 2 will be considered the main statistical method in handling cross-overs via a time-dependent variable in Cox model. The other 2 methods are considered as sensitivity analyses.

Differential treatment effects for the primary endpoint and major secondary endpoints of interest using on-treatment analyses will also be conducted. Subgroups of interest will include those listed in section 8.1.

Because treatment assignment is no longer random, results can be biased by an association between the likelihood of treatment change and the risk of a clinical event (i.e., factors that make a patient more likely to cross over may also make them more likely to have an event). Thus, such analyses will be cautiously interpreted. Each of the analyses described in this section will be covariate adjusted using the covariates described in section 8.1 for the primary endpoint.

11. Per-Protocol Analysis

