Using the methods described for the primary endpoint in Section 8, an analysis will also be performed to compare the primary endpoint and the key secondary clinical outcomes of the two treatment strategies among the subset of patients who fully satisfied the inclusion/exclusion criteria and received the treatment to which they were randomly allocated. This analysis will include patients randomized to the drug arm who were treated with drug therapy, and patients randomized to the ablation arm who underwent the ablation within 6 months following enrollment in the trial. The follow-up of drug-arm patients who crossed over to ablation will be censored at the time of the ablation. Patients randomized to the ablation arm who were not ablated within 6 months will be excluded from this analysis. Additional sensitivity analyses will be performed in which the window for ablation is varied to include a shorter interval (3 months) and a longer window (1 year).

The analyses outlined in Sections 10 and 11 will be strictly supplementary to the intent-to-treat analyses described earlier.

12. Multiple Comparisons

With the primary hypothesis and the various secondary endpoints that have been outlined, there is a multiplicity of analyses to be performed, which leads to an increased probability that at least one of the comparisons could be "significant" by chance. There are adjustments (e.g., based on the Bonferroni inequality) that could be used to preserve the overall type I error level. To attempt to adjust for the effects of the repeated significance testing that will occur as part of the interim monitoring (discussed below), plus adjust for the multiplicity of secondary endpoints, would require that very small significance levels be used for every comparison. The overall level of significance will be 0.049 for the assessment of the primary endpoint (see Section 13) and 0.05 for all secondary endpoints. However, to account in part for the multiplicity of comparisons involving secondary endpoints, we will be conservative in the interpretation of the analyses, taking into account the degree of significance, and looking for consistency across endpoints. The actual p-value for each comparison will be reported to aid in the overall interpretation. We have

also pre-specified the primary and secondary outcome variables to avoid over-interpretation of strictly exploratory comparisons.

13. Interim Analyses

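### The per-protocol analysis in SAP Section 11 counts time from randomization but admits ablation-arm patients only if later ablated, so early events that prevent ablation are deleted from that arm alone

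*SAP*

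**What the plan says.** SAP Section 11 (Per-Protocol Analysis) takes its methods from Section 8: "Using the methods described for the primary endpoint in Section 8, an analysis will also be performed to compare the primary endpoint", together with the key secondary outcomes. Section 8 defines time as the date of the first event minus the date of randomization, and Section 11 sets no other time origin.

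The entry rules differ by arm:

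- Drug arm: "This analysis will include patients randomized to the drug arm who were treated with drug therapy". There is no time window. For crossovers, "The follow-up of drug-arm patients who crossed over to ablation will be censored at the time of the ablation".
- Ablation arm: the procedure must take place within 6 months of enrollment. "Patients randomized to the ablation arm who were not ablated within 6 months will be excluded from this analysis". Sensitivity versions use 3 months and 1 year.

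The status of the analysis is clear: "The analyses outlined in Sections 10 and 11 will be strictly supplementary to the intent-to-treat analyses described earlier".

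On the wait itself, Protocol 11.1 strongly encourages less than 2 weeks from randomization to ablation. SAP 7.2 will report by arm how many received the assigned treatment, and how many ablation-arm patients never had an ablation. It describes follow-up before crossover in the drug arm. It does not list the wait to ablation in the ablation arm, or the events during that wait.

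**The concern.** An ablation-arm patient who dies on day 10 while waiting cannot meet the entry condition and disappears. A treated drug-arm patient who dies on day 10 is counted. The same holds for a non-fatal stroke, bleed or arrest that leads to the procedure being abandoned. A non-fatal event followed by ablation inside the window stays in. The ablation arm thus carries a stretch of guaranteed event-free time that the drug arm lacks.

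Protocol 8.1 allows for 25-30% drug-arm crossover, so readers are likely to look to the per-protocol result for the effect of actually receiving ablation. A per-protocol HR slightly below the ITT HR could be read that way when the entry rule alone produces it. For mortality, every pre-procedure event is fatal, so every one is deleted.

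**Working it through.** **Starting figure.** The documents give no figure for this analysis. To confirm the event-rate inputs, take the design power in Protocol 8.1: hazard λ = −ln(1 − 0.12)/3 = 0.0426 per year, HR 0.70, 4-year uniform accrual, 3-year minimum follow-up, 2% loss. This gives 355 events for 2,200 patients. Power is Φ(√355 × |ln 0.70|/2 − 1.96) = 91.9%, against the stated 90%. For 2,000 patients it is 322 events and 89.3%, against 88%. The inputs are sound.

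**Inputs from the documents.** 2,204 patients randomized 1:1, so 1,102 per arm; minimum follow-up about 2 years and median about 4 (SAP introduction), taken as uniform over 2-6 years; 12% 3-year rate; 28% crossover by 4 years, within the 25-30% of Protocol 8.1.

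**Assumed.** Exponential waits with means of 14, 30, 60 and 90 days; 5% never ablated (the pilot had 1 of 29); no treatment effect; crossover and waits unrelated to risk.

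**Deleted events.** With mean wait m and window W in years, and every earlier event preventing ablation, deleted ≈ 1,102 × 0.95 × λ × [m − (W + m)e^(−W/m)], where 1,102 × 0.95 × λ = 44.6 per year.

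- 14 days: m = 0.0383 and the tail is negligible, so 44.6 × 0.0383 = 1.7.
- 90 days, 6-month window: m = 0.2464 and e^(−W/m) = 0.1315, so 44.6 × (0.2464 − 0.7464 × 0.1315) = 44.6 × 0.1483 = 6.6.

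**Kept events.** The chance of an event in follow-up is 1 − (e^(−2λ) − e^(−6λ))/(4λ) = 0.1557, and 1,102 × 0.95 × 0.1557 = 163.0. At 14 days, 163.0 − 1.7 = 161. At 90 days, 163.0 × (1 − 0.1315) − 6.6 = 135.

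**Hazard ratio.** The crude ratio kept/(kept + deleted) is 161.3/163.0 = 0.990 at 14 days and 135.0/141.6 = 0.953 at 90 days. Solving the Cox score equation gives slightly lower values, because crossover censoring thins the drug arm later and gives early follow-up more weight.

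| Mean wait (days) | Deleted | Kept | HR, all earlier events prevent ablation | HR, 60% prevent it | Bias in SE (all prevent) |
|---|---|---|---|---|---|
| 14 | 1.7 | 161 | 0.989 | 0.993 | 0.10 |
| 30 | 3.6 | 159 | 0.976 | 0.986 | 0.21 |
| 60 | 5.9 | 149 | 0.959 | 0.975 | 0.36 |
| 90 | 6.6 | 135 | 0.950 | 0.970 | 0.43 |

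For mortality at an assumed 6% 3-year rate, the HR is 0.989 at 14 days and 0.952 at 90 days.

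**Windows.** At 90 days the 3-month, 6-month and 1-year versions give 0.970, 0.950 and 0.933. At 14 days all three give 0.989. Lengthening the window can enlarge the bias, and no window removes it.

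**Opposing force.** Suppose half the patients have a 2- to 3-fold hazard and cross over 1.5 to 2 times as often (assumed). Censoring crossovers then gives 1.011-1.028 by itself, and the net 6-month HR is 1.000-1.017 at 14 days and 0.960-0.976 at 90 days. If the higher-risk half crosses over less often (ratio 0.67 or 0.5), crossover censoring alone gives 0.973-0.989 and adds to the deletion.

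**The case against.** The strongest reply is about size. The only wait in the documents is the encouraged 2 weeks, where the bias is about 1% and 0.1 SE. The 90-day case drops about 18% of the arm (5% + 0.95 × 13.15% + 6.6/1,102), whereas the pilot ablated 28 of 29. The 0.95 also assumes that every earlier event prevents ablation. All of this stands: 60 and 90 days are stress cases and the all-prevent column is an upper bound.

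A second reply is that the repair can worsen the total error. That also stands. If higher-risk patients cross over more, the present rule nets about 0.99-1.02 at 14 days and the repaired one about 1.00-1.03. If higher-risk patients are ablated sooner (2-fold hazard, 90-day mean wait, 3-month window), the present rule gives about 1.00-1.03 and the repaired one about 1.03-1.06. If they wait twice as long, the repair helps (0.91 to 0.94). Two errors that may partly offset still do not make an interpretable estimate.

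A third reply is that the repair changes the question. It does: the analysis becomes one of a strategy with a grace period.

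A reader might also infer that Section 10 methods 1 and 3 settle the matter. They do not delete these events; for example, "Method 3 has the ablation variable started as 1 for patients who were randomized to ablation". But they move crossovers into the ablation group, so they compare something different. Under the same risk-related crossover they give 1.017-1.047. Disagreement with Section 11 would not isolate this bias. Nor is agreement with the main on-treatment analysis independent support. "Among the 3 methods described above, method 2 will be considered the main statistical method", and "In method 2, the ablation variable starts as 1 for all patients who were randomized to ablation and actually received ablation", so it too conditions on reaching the procedure.

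**Conclusion.** The flaw is in the stated rule and follows directly from SAP Sections 8 and 11: a randomization clock, entry conditional on a later procedure in one arm, and no such window in the other. Taken alone it favours ablation, by about 1% on the HR at a 14-day mean wait and 3-5% in a 90-day stress case. These sizes rest on assumed waits and an assumed share of early events that prevent ablation. Similar results across the three windows would not show that the bias is absent.

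Two stronger readings are tempting. One is that the per-protocol HR as a whole must lean toward ablation. The documents do not support this: SAP Section 10 itself warns that patients likelier to cross over may be likelier to have an event, and censoring them can push the other way. The other is that the trial's main conclusion is at risk. It is not: ITT is the primary analysis and Section 11 is only supplementary. Priority is minor to moderate.

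**What to change.** In each window version (3 months, 6 months, 1 year), keep all eligible ablation-arm patients from randomization, count their events up to the end of the window, and censor at the window those who are event-free and still unablated. When waits and crossover are unrelated to risk, this returns an HR of 1.000 under the null.

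If the sponsor prefers the present population, retain it as a labelled sensitivity analysis with a caution about guaranteed event-free time in the ablation arm.

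In either case report, for the ablation arm, the distribution of time from randomization to ablation, the number not ablated in each window, and their primary events and deaths. That table alone lets a reader judge the size.

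The cost is SAP wording, a few lines of code and one table, with no new data. The SAP should state the downsides. The change removes only this deletion. Some events before any ablation will count in the ablation arm. Censoring at the window may be informative, and crossover censoring and risk-related waits stay uncorrected. Where those act in the opposite direction, the repaired HR can lie further from 1 than the present one.
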